Clinical trial monitoring will be conducted to ensure that the rights and well-being of human subjects are protected, to verify that the reported clinical trial data are accurate, complete and verifiable from source documents and to verify that the conduct of the trial is in compliance with the currently approved protocol/amendment(s), with Good Clinical Practices and with the applicable regulatory requirements.

Safety criteria for removing a subject from the study in the period before the end of the 5-day ambulatory pump use:

Prior to and during the popliteal nerve block and catheter placement: Subjects with a failed peripheral nerve block will not have a catheter placed and will not be included in the study (see Exclusions, below). Subjects will be discontinued and the catheter removed if there is inadequate view of the popliteal nerve under ultrasound guidance, paresthesias that do not resolve before the local anesthetic from the nerve injection takes effect, blood is present in the catheter during insertion indicating possible vascular injury, or one or more signs of local anesthetic systemic toxicity (LAST) (ringing in ears, metallic taste in mouth, lightheadedness, seizure, or cardiac compromise).

During Surgical Procedure and General Anesthetic – Subjects will be discontinued if there are one or more signs of LAST (listed above) or the catheter is inadvertently removed during the operation.

During immediate postoperative period in PACU – Subject will be removed if there are one or more signs of LAST (listed above) or if the catheter is removed inadvertently

After Discharge for period the pump is used: Based on the daily phone contacts, subjects will stop using the pump if there are, signs of local infection(after evaluation by the Acute Pain Service; subject would be called back into the hospital), or one or more signs of LAST (listed above). Subjects who experience paresthesias that cause them discomfort, or weakness that prevents them from participating in physical or occupational therapy, will be asked to return to the clinic for evaluation by an anesthesiologist. If these issues cannot be resolved (e.g. by lowering the dose), these subjects will have the catheter and pump removed. Subjects who must remove the pump early for any reason will be retained in the study for purposes of answering the pain surveys.

Defining and Reporting of Adverse Events:

Adverse event Definitions:

Adverse Event

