Fatigue	No interference with activity	Some interference with activity	Significant; prevents daily activity	ER visit or hospitalization
Myalgia	No interference with activity	Some interference with activity	Significant; prevents daily activity	ER visit or hospitalization

Table 9.4 extracted from: Guidance for Industry, Toxicity Grading Scale for Healthy Adult and Adolescent Volunteers Enrolled in Preventive Vaccine Trials, U.S. Department of Health and Human Services, Food and Drug Administration, Center for Biologics Evaluation and Research, August 2016

Treatment of cardiovascular and neurologic adverse events

- Local anesthetic systemic toxicity
 - Treatment will be initiated as recommended as the American Society of Regional Anesthesia and Pain Medicine, according to the society's checklist

Treatment will include: transfer to intensive care unit setting if not already in intensive care unit, continuous hemodynamic monitoring for at least 24 hours, appropriate airway management with assistance from respiratory therapy and a critical care consultant as needed, cardiovascular stabilization and assistance from a critical care consultant as needed, administration of Lipid Emulsion therapy, as per ASRA checklist in Appendix, Neurology consult for any observed systemic

neurologic toxicity (including change in vision, mental status change, persistent headache, seizure), Cardiology consult for any arrhythmias that persist greater than 30 minutes, beyond initial appropriate medical treatment, or result in hypotension with systolic blood pressure < 80mmHg.

Every adverse event, whether or not thought to be related to study drug, will be recorded and entered into the Medidata Rave® Case Report Form database.

Any medical condition present prior to study enrollment should not be reported as an adverse event, unless the medical condition worsens in severity or seriousness during the study. In this case it may be reported as an adverse event at the discretion of the Investigator.

The Investigator will review each event and assess its severity and relationship to the study treatment.

Criteria for stopping the study early:

Because this is a small study, criteria for stopping the study will not be based on statistical analysis but rather on the occurrence of any of the following serious adverse events in any of the subjects randomized to receive the ropivacaine pumps:

During immediate peri-operative period after pump has been connected:

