 A single serious adverse event of LAST requiring rescue medication, cardiac resuscitation, or transfer to the ICU.

During the 5 day period of ambulatory pump use:

 A single serious adverse event of catheter site infection requiring hospital admission.

 A single serious adverse event of LAST requiring hospital admission.

During the entire study period:

 A single serious adverse event of any life-threatening adverse event deemed possibly related to the use of the ropivacaine pump.

 Two subjects receiving pumps experiencing moderate adverse events of tinnitus and/or metallic taste in the mouth.

11. Data Safety monitoring plan and/or DSMB:

As discussed in section 6, the medical monitor, [name], will review subject's research data and adverse events to ensure patient safety.”

12. Data Analysis:

The primary outcome measure is SEFAS scores at the indicated time points. A secondary outcome measure is use of opioids in the immediate postoperative period.

Each SEFAS response has 5 ordinal response choices scored 0 through 4, with the lowest score (0) representing the most severe disability and the highest total score being 48. If subjects omit a question the score will be re-normalized; however, the Redcap interface will be designed to try to obtain an answer for each question. The Mann-Whitney test will be used to examine differences in the SEFAS scores at each time point. For analysis of SEFAS scores, the pilot study sample size of 20 per group is sufficient for detecting a difference in scores between groups of 9 points with a power of 0.8 and $\alpha = 0.05$ (using the standard deviation obtained from SEFAS use in an ankle surgery study[35]); this score would represent moving up one rank in 3/4 of the questions which would be a functionally meaningful improvement given the 0 – 4 ordinal scale employed. . Patients who are withdrawn from the study due to failure of the initial nerve block (see above) will be considered as screening failures; no follow-up data or questionnaire scores will be obtained. We consider that such a failure is unlikely to have any relationship to the chronic pain outcome we are studying. The same approach will be taken for patients who decide to withdraw from the study, or are withdrawn by the attending surgeon or anesthesiologist, after randomization but before the single shot nerve block procedure.

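### The tinnitus and metallic-taste stopping trigger asks for moderate events under a lead-in limited to serious ones, and does not say moderate or greater

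*Protocol*

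**What the plan says.** Protocol Section 10, under Criteria for stopping the study early, rejects a statistical rule because the study is small. Stopping depends instead "on the occurrence of any of the following serious adverse events in any of the subjects randomized to receive the ropivacaine pumps". Five triggers follow under three time headings:

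- Under "During immediate peri-operative period after pump has been connected": one case of LAST that needs rescue drugs, resuscitation or a move to intensive care.
- Under the heading for the five days of pump use: one admission for an infected catheter site; and "A single serious adverse event of LAST requiring hospital admission".
- Under "During the entire study period": one life-threatening event "deemed possibly related to the use of the ropivacaine pump"; and "Two subjects receiving pumps experiencing moderate adverse events of tinnitus and/or metallic taste in the mouth".

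Earlier in Section 10, the safety criteria for removing a subject give the signs of LAST as "ringing in ears, metallic taste in mouth, lightheadedness, seizure, or cardiac compromise". The two symptoms in the last trigger are therefore recognised signs of drug toxicity.

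**The concern.** The last trigger is the study's early-warning rule. It is the only one of the five that can fire without rescue treatment, intensive care, hospital admission or a threat to life. Because the rules are expressly non-statistical, their wording is the whole rule.

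That wording has two faults. The lead-in and the trigger use different scales, seriousness and severity, so it is unclear whether an ordinary moderate case counts at all. The trigger also names one grade and does not add *or greater*, so read literally it lapses as symptoms worsen. What is at stake is whether a repeated toxicity signal in the pump arm stops the study by rule or only through someone's discretion.

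**Working it through.** The plan gives no operating characteristic for this rule, so there is no figure to reproduce. The check sets the definitions side by side and then applies the triggers to cases.

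**Step 1. The two scales.** Section 10 defines serious by outcome: death, threat to life, hospitalization, lasting incapacity or birth defect, plus important medical events by judgment. Table 9.4 makes moderate Grade 2, severe Grade 3 and potentially life-threatening Grade 4. As it reads in the text available, the table has no row for tinnitus or taste, so the grade rests on the investigator's own assessment. A moderate case would be serious only exceptionally, mainly through the important-medical-event clause.

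**Step 2. Does the lead-in govern?** Four of the five triggers repeat the word serious in their own text; 5 − 4 = 1 does not, and it is this one. If the lead-in governed, the trigger would have almost no work of its own. A toxicity case made serious by admission or threat to life would normally fire one of the single-case triggers first. The authors therefore probably meant moderate, non-serious cases to count. The text does not say so.

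**Step 3. Cases, read literally.** In cases A to C the pump is stopped at home on day 2, with no admission and no threat to life.

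| Case | Lead-in governs | Lead-in does not govern | After the fix |
|---|---|---|---|
| A. Two subjects, severe tinnitus | 0 of 5 met | 0 of 5 met | met |
| B. One severe and one moderate | 0 of 5 met | 0 of 5 met | met |
| C. Two subjects, moderate and not serious | 0 of 5 met | 1 of 5 met | met |
| D. One subject, severe, treated as LAST with transfer to intensive care | LAST admission trigger met | LAST admission trigger met | unchanged |

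In A and B the result does not depend on the lead-in, because a severe event is not in the moderate category.

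**Step 4. Can case A arise?** Two places in Section 10 suggest so. In the Table 9.4 rows for headache, fatigue and myalgia, Grade 3 covers a symptom that prevents daily activity, while an emergency visit or hospitalization belongs to Grade 4. By analogy, severe without admission is an ordinary category on this scale. The rule after discharge reads "subject would be called back into the hospital), or one or more signs of LAST (listed above"; the recall to hospital stands inside the parenthesis on infection, and for signs of LAST the sentence requires only that the pump stop. Against this, the section on treating LAST includes transfer to intensive care. The documents do not settle which route a subject with tinnitus at home would follow, so case A is possible but not certain.

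**The case against.** The strongest reply is that nobody applying a safety rule would treat severe tinnitus as falling short of a moderate threshold, and that severe tinnitus during infusion would be managed as LAST. One subject would then fire the admission trigger before a two-subject rule mattered. The intent is probably as described, and case D concedes the second part. But if every such symptom went to intensive care, one case would already stop the study and a two-subject trigger would be pointless. The trigger therefore presupposes that at least some cases are handled short of admission. Where an individual severe case would go remains open.

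It is also true that individual protection is intact and that the medical monitor can halt enrollment (Protocol Section 6). That limits the harm. It does not repair a pre-specified rule whose purpose is not to depend on discretion.

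A reader might go further and infer that the trigger has the wrong time window: the heading covers the entire study, so unrelated tinnitus months after a five-day infusion could stop the trial. The documents do not support this as a material risk.

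- It is the only trigger that needs two subjects, and its heading is the only one of the three under which a peri-operative case and a case at home can be added together.
- The wide window includes the infusion, so it misses no toxicity.
- The adverse event definition asks for a temporal association with drug use, which is doubtful for a late case even though no causal judgment is required.
- Later contacts cover the SEFAS and medication use, and chart review runs for up to 3 months after pump use (Section 6), so late cases would seldom be collected.
- Section 1 allows 18 months for data collection. Taking off 12 months of follow-up leaves about 6 months of enrollment (an inference), so many late cases would come when little or no enrollment is left to stop.

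The documents give no background rate for these symptoms, so no probability of a spurious stop can be stated. Comparing five days with a year gives a ratio of durations, which does not measure impact.

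**Conclusion.** The concern holds as a wording defect with two parts: the lead-in and the trigger conflict on seriousness, and the trigger omits *or greater*. Its size is best expressed by the cases. Two severe cases managed at home, or one severe and one moderate, meet 0 of 5 triggers under either reading. Two moderate, non-serious cases meet 0 or 1 of 5, depending on how the lead-in is read.

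This rests on a literal reading and, for the severe cases, on management by stopping the pump without admission. If they are treated as LAST with intensive care transfer or admission, the LAST trigger closes the gap. It would be wrong to infer that subjects are left unprotected, since any sign of LAST stops that subject's pump. The onset window is at most a minor point of clarity. The correction is worth making because it is cheap and concerns safety; nothing here shows that the study is unsafe.

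**What to change.** Make two edits to Protocol Section 10:

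1. In the lead-in, delete *serious*, so that it refers to any of the adverse events that follow. The other four triggers carry the word in their own text and keep their meaning.
2. Replace the last trigger with: *Two subjects receiving pumps (counted across the whole study) who have tinnitus, metallic taste or both, of moderate or greater severity, whether or not the event meets the definition of serious.*

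Severity stays with the investigator, as now. The cost is one word deleted and one sentence rewritten, with no new data and essentially no downside.

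Optionally, the clinicians may limit onset to the period from pump connection until shortly after the actual end of infusion, with the length of that tail theirs to set. Two consequences should be accepted knowingly. The pump is connected right after the single injection that both arms receive, so toxicity from that injection could count. Events starting after the window would be left to the medical monitor. Adding the neighbouring trigger's relatedness condition is not needed, and it would bring unblinded investigator judgment into the rule.

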In the experimental group, in addition to the standard single shot nerve block, subjects will receive a catheter to deliver continuous 5 day popliteal sciatic nerve block using a disposable ambulatory pain pump. The catheter will be inserted starting just prior to surgery. This procedure is readily added on to the procedure for single injection, which involves ultrasound (and in some cases nerve stimulation) guidance for insertion of a needle near the sciatic nerve at the popliteal fossa. As part of standard care for administering a peripheral nerve block, sedatives are administered on as needed basis. Typically the patient will receive midazolam 1 mg every 5 minutes as needed. The catheter is inserted

just after the nerve block injection, during the same procedure and using the same needle placement. If there is a major vascular injury during the catheter placement (placement of the peripheral nerve catheter into the artery as confirmed by withdrawal of blood from the catheter itself), the catheter will be withdrawn and the subject will not receive a pump. An ambIT portable pump (as currently used in the participating hospitals after some other types of surgeries) will be attached to the catheter at the time the block is placed, and continuous block with 0.2% ropivacaine will begin immediately after surgery. The drug delivery rate will be 6 mL/hour. An 800 mL bag of medication will be provided to the subjects to allow medication for a 5 day period without requiring the subject to return to the clinic for refill. This drug delivery rate is on the lower end of the range commonly used in our hospitals for patients taking home pumps after other types of surgeries, which are usually started at 8 mL/hour with the option of patient controlled boluses. Previous clinical studies examined infusion rates of 6 to 14 mL/hour. The lower, fixed rate was chosen for this study to help avoid toxicity, since the duration of the pump is longer than commonly used at our hospitals. The goal based on preclinical studies is to block abnormal spontaneous activity from the sensory nerves, which requires a lower dose than complete sensory block. The selected infusion rate should also avoid motor block. The daily dose will be 384 mg; the FDA data sheet [19] indicates that a cumulative dose of up to 770 mg over 24 hours is well tolerated and studies indicate that the peak systemic levels during prolonged infusion occur after approximately 3 days[12].

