- pregnancy (ropivacaine is FDA pregnancy category B; pregnancy test is routine part of the surgical procedure unless the woman signs a waiver; patients who sign such a waiver instead of having a pregnancy test will not be eligible for the study, unless their medical record clearly indicates they have had a hysterectomy or tubal ligation.)
- lactating
- have heart disease or heart rhythm disorder or taking anti- antiarrhythmic drugs
- severe renal impairment (Class 3 or worse kidney disease)
- liver disease (cirrhosis or liver failure)
- ever had an allergic reaction to any type of local anesthetic
- taking therapeutic doses of anti-coagulants or anti-platelet therapy (prophylactic doses started because of the hospital admission are not an exclusion)
- taking antidepressants or other psychiatric medications (due to drug interaction risk per the ropivacaine data sheet)
- single shot local nerve block prior to surgery was ineffective (rare; see below)
- selected for neuraxial anesthesia rather than general anesthesia for the open reduction surgery (rare)
- already receiving chronic analgesic therapy for a separate chronic pain condition

Rarely, the single shot local nerve blockade given prior to surgery as standard-of-care is found to be ineffective, and surgery proceeds using only general anesthesia. The ineffectiveness of the single shot would indicate that the catheter placement was also likely to be ineffective. For such patients, the

catheter will be removed before the surgery and they will be removed from the study; attempting to re-position and re-test the catheter outside of the standard-of-care procedures was deemed to be undue risk. Patients with failed nerve block who were not randomized to receive the pump will also be removed to avoid bias in the analysis, and because the lack of the single nerve block might also have effects on the development of chronic pain.

Because the treatment period lasts only 5 days, patients who may possibly become pregnant during that time are allowed to participate.

15. Consenting process and plan

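### Adverse-event follow-up is not assured for pump-arm subjects whose catheter is inserted and who are then removed from the study before discharge

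*Protocol*

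**What the plan says.** Consent and randomization come before surgery (protocol section 7, Encounters). In the experimental arm, section 6 has the catheter inserted "just after the nerve block injection, during the same procedure and using the same needle placement", with bag and pump connected at that point. The infusion starts only in the PACU.

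If the single-shot block proves ineffective in such a subject, section 14 states that the "catheter will be removed before the surgery and they will be removed from the study". Section 12 says that patients withdrawn for failure of the initial block "will be considered as screening failures; no follow-up data or questionnaire scores will be obtained". SAP D1 repeats this rule.

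Section 10 adds three relevant statements:

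- On reporting: "Every adverse event, whether or not thought to be related to study drug, will be recorded". No exception is made for withdrawn subjects, and no collection window is given.
- In the safety criteria for removal: "Subjects with a failed peripheral nerve block will not have a catheter placed and will not be included in the study".
- In the same criteria, subjects are discontinued for an inadequate ultrasound view, unresolved paresthesias, blood in the catheter, signs of local anesthetic systemic toxicity (LAST), or accidental loss of the catheter. For the PACU the wording is "Subject will be removed if there are one or more signs of LAST". The only subjects expressly retained are those who take the pump off early, and the stated purpose is the pain surveys.

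**The concern.** Catheter placement is the step that the control arm does not receive. Read together, these sections let a randomized subject undergo it and then be reclassified as someone who never entered the trial. Events that appear after removal, such as a site infection or a paresthesia that does not clear, may then have no defined route into the study database.

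What is at stake is the harm record, not the SEFAS comparison; section 14 removes failed-block subjects from both arms. The stopping criteria in section 10 apply to all subjects randomized to the pump, and one of them runs for the whole study. A removed subject belongs to that population, yet the plan does not say how that subject's later events would be found. A complication rate calculated only on subjects who kept the catheter would also leave out the placements that went wrong.

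**Working it through.** The plan states no figure on this point, so the check is mainly a comparison of passages. A short calculation at the end gives the scale.

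**1. Can a removed subject have been exposed?** Under sections 6 and 14, yes: randomization, block injection, catheter inserted and pump connected, block found ineffective, catheter removed before surgery, subject removed. Under the section 10 removal criteria, no, because a failed block means that no catheter is placed. The two accounts conflict.

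**2. What is said about each catheter-exposed group removed early?**

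| Group | Status | Adverse-event follow-up after removal |
|---|---|---|
| Block failure, catheter removed (section 14) | Screening failure, no follow-up data (section 12, SAP D1) | Not stated |
| Discontinued at placement, in surgery or in PACU (section 10) | Discontinued or removed | Not stated |
| Pump taken off early (section 10) | Retained for surveys | Not stated as such, but still in the study |

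The no-follow-up rule names two groups: block failures, and withdrawals after randomization but before the block. The second group never has a catheter. The rule does not name the middle row of the table, where the plan is simply silent.

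**3. Do the safety routes reach these subjects?**

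- *Adverse-event rule (section 10).* Unqualified, so events up to withdrawal must be recorded. Nothing says how long it runs afterwards.
- *Chart review (section 6).* At least monthly, for enrolled experimental-group patients, up to 3 months after use of the pumps. It is not said whether a screening failure still counts as enrolled. If the infusion never started, the 3-month window has no clear starting point.
- *Daily calls (section 6).* Described as monitoring analgesic use, toxicity, infection and pump problems, with reminders about catheter removal. Whether a removed subject is called is not said.
- *SAP sections E and I.* Wound healing and re-operation are listed. There is no adverse-event variable, no adverse-event table and no denominator for catheter harms.

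**4. Scale.** Input from the documents: up to 60 enrolled. Assumptions: half in the pump arm, 60/2 = 30, and a failure rate p of 1% to 10%, because the documents say only that failure is rare. Expected failures = 30p; chance of at least one = 1 − (1 − p)^30.

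| p | Expected failures | Chance of at least one |
|---|---|---|
| 1% | 0.3 | 26.0% |
| 2% | 0.6 | 45.5% |
| 5% | 1.5 | 78.5% |
| 10% | 3.0 | 95.8% |

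For a rough ceiling on expected complications in these subjects, add the upper rates in section 10 for bleeding, local infection and short-term paresthesia: 0.4% + 3% + 1.5% = 4.9%. Multiplying by the expected failures gives 0.3 × 0.049 = 0.015, 0.6 × 0.049 = 0.029, 1.5 × 0.049 = 0.074 and 3.0 × 0.049 = 0.147 events. This overstates the loss. Bleeding and paresthesia at insertion occur before withdrawal, so the adverse-event rule covers them, and section 10 says that infection risk rises with duration of catheter use.

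**The case against.** The strongest reply is that the rules are compatible. The no-follow-up sentence sits in the SEFAS paragraph of section 12 and under Aim 1 of the SAP. Both documents say nearby, in discussing loss to follow-up, that follow-up consists only of questionnaires. On that reading the sentence stops SEFAS collection and leaves the adverse-event rule untouched. Much of this stands. A reader might infer that catheter harms go unrecorded, or that section 12 contradicts section 10, and the documents support neither statement. However, the sentence names follow-up data and questionnaire scores as separate items, so a wider reading is open to site staff, and no passage closes it.

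Three other inferences go too far:

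- *That the no-follow-up rule also covers the section 10 removals for LAST, blood or paresthesia.* It does not name them. LAST needing rescue medication, resuscitation or ICU transfer after pump connection is itself a stopping criterion.
- *That removed subjects lose all monitoring.* The chart review may still apply. Section 15 keeps withdrawn subjects in standard follow-up appointments, and the medical monitor reviews adverse events.
- *That the likely loss is one complication, 1/30 = 3.3 percentage points, or 1/20 = 5.0.* That is the weight of one event if it happens, not its expected size. The 20 per group is the evaluable number, reached after such subjects are excluded.

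Nor do the documents say that this is the first use of the catheter for this indication at these hospitals. Section 6 says only that it is not routine for ankle fracture surgery.

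Finally, under the section 10 wording the block-failure case would not arise. That reduces the point but does not remove it, because section 14 says otherwise and the section 10 discontinuations remain.

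**Conclusion.** The point holds in a limited form. Under sections 6 and 14, a randomized subject can have the catheter inserted and removed, and section 12 and SAP D1 then call that subject a screening failure with no follow-up data. Recording of events up to withdrawal is required. Capture of later ones is not assured, because no passage gives a window or says that the chart review and calls continue. The same silence applies to other catheter-exposed subjects discontinued before discharge. Separately, sections 10 and 14 contradict each other on whether a failed-block subject has a catheter placed.

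The size is small: 0.3 to 3.0 block failures among about 30 pump-arm subjects, and at most about 0.15 expected complications among them. Both figures rest on assumed failure rates, and the upper end fits poorly with a failure described as rare. Section 10 discontinuations would be additional, at a rate that the documents do not give. The change is worth making because it is cheap and makes both harm ascertainment and its denominator explicit.

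**What to change.** 1. Reconcile the removal criteria in protocol section 10 with section 14 on whether a failed-block subject has a catheter placed.
2. In protocol sections 10, 12 and 14 and in SAP D1, state that the no-follow-up rule concerns SEFAS only. State also that any subject with an attempted catheter insertion stays in adverse-event follow-up, through the existing chart review and safety contacts, for a stated window, unless consent is withdrawn.
3. Start that window at the insertion attempt, so that it is defined when no infusion is given.
4. Report catheter harms with all insertion attempts as the denominator, and add the corresponding variable and table to SAP sections E and I.

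The cost is wording in both documents plus a few extra calls and chart reviews by existing staff. Section 6 says that the consent form already allows access to records for complications. The downside is that the reported complication rate may look slightly less favourable.
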